#### **IV. RESEARCH STUDY DESIGN**

---

**Overview and Design of the Proposed Study.** Consistent with our preliminary study, we will recruit (from the Denver and Boulder areas): 450 participants who report a desire to use marijuana to cope with their anxiety, have had previous experience with marijuana, and report a Generalized Anxiety Disorder-7 (GAD-7) score of  $\geq 5$  (at least mild to moderate anxiety) and 75 non-using cannabis controls (matched for anxiety via GAD-7  $\geq 5$ ) who do not report an intention to use marijuana to cope with their anxiety nor any marijuana use over the prior six months. A summary of the Assessment schedule and the additional inclusion/exclusion criteria are detailed below in Table 1 and Section VI (respectively).

All participants will come to the CUChange Lab for a Baseline Appointment (Session 1) involving extensive measures of anxiety (e.g., Depression, anxiety, and stress scale, a rumination induction task, a dot probe task, rumination self-report scale, etc.) and other psychiatric symptoms, health behavior (e.g., stress, quality of life, sleep, alcohol use), the cognitive testing battery utilized in our preliminary studies, a blood draw for biomarkers of inflammation, and a motor battery (**Baseline Appointment, Session 1**). During this Baseline Appointment, a research assistant will provide information on three at-home aspects of the study: 1) the range of assigned cannabis products (e.g., differing THC to CBD ratios possible) and potential prices, 2) the ActiGraph wearable watch device that participants will be loaned to measure physical activity and sleep (during the final 2 weeks of the four week study), and 3) a microbiome collection kit that they will be given to complete (once before and once after 4 weeks of *ad libitum* use of their cannabis product). The experimental aspect of this study will be the assigned cannabis ratio, while the other aspects of this study are *ad libitum* based, with regard to the dosing schedule and choice of product type (flower or edible), by participants that would already like to use cannabis to cope with their anxiety.

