**Marijuana Administration at Home.** Unlike other studies done in the United States to date, the proposed work will utilize a design that allows participants to choose their type of administration and *ad libitum* dosing schedule, but contains an experimental element (i.e., strain assignment). Specifically, at the end of the baseline session, participants will be given instructions to purchase assigned strain, differing by THC to CBD ratio (n=75/flower strain; n=50/edible strain): 1) a THC-based strain akin to a typically used strain with normal levels of THC and little to no CBD (+THC/-CBD), 2) a 1:1 strain with equivalent THC and CBD levels (+THC/+CBD), or 3) a CBD-enriched strain with little to no THC (-THC/+CBD) at a good clinical practice dispensary in Boulder or Denver, Colorado.

The market for flower versus edible cannabis products are similar, but differ slightly in their servings, typical doses, and labeling system (potency listed by percent with flower products rather than by mg with edibles) making it currently impossible to assign identical flower and

edible potency groups, or ratios. However, Colorado requires all strains to be tested by a state licensed lab, which allows us to have a precise measure of potency to operationalize our strain assignments. Therefore, the flower groups will be assigned either the +THC/-CBD strain (containing 18% THC and <1% CBD), a combination of THC and CBD strain (a 1:1 ratio +THC/+CBD containing 12% THC and 12% CBD), or the -THC/+CBD strain (containing <1% THC and 18% CBD). Like the flower group, the edible groups will be assigned to one of the same ratios (an all THC strain, a combination of THC to CBD strain with a 1:1 ratio, or an all CBD strain) and they will choose when and how much they would like to use this assigned edible over the next four weeks. However, the participants that choose to be in the edible group (rather than the flower group), will be assigned an edible product with 10 mg of THC, CBD, or a combination of THC and CBD per edible piece (comparable to the flower products with 6, 12, or 18% THC, CBD, or a combination of THC and CBD).

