The dispensary will set aside a specific lot of each flower (to be smoked or vaporized) and edible form of the assigned strain, which will be packaged in childproof bottles and labeled as “Strain C”, “Strain D” or “Strain E”, such that participants and dispensary staff will be blind to the ratio assignment until the product is purchased (THC and CBD content will be printed on the label, as required by state law), and the research staff will remain blind to which strain was assigned until after data analysis. [name] (co-investigator) will maintain the blind during the study period. The instruction to purchase “C”, “D” or “E” will be randomized across participants such that equal numbers of male and female participants are included across the ratio conditions. The design involves the instruction that participants can use as little or as much of the marijuana as they wish over the course of the four weeks of the study, and are asked not to use any other strain during that time (but if so, to just report what was used). Therefore, a research assistant will give participants that are marijuana users, a card with directions to a local dispensary. The card will have instructions to purchase a particular strain of cannabis (e.g., “strain C”) but participants will choose the amount of cannabis that they expect to use during the study (i.e., we will not assign a specific amount for them to purchase or to use during the 4-week study period). While the potency may vary slightly by the strain assignment and the amount used may vary by each person, we expect approximately one gram of flower cannabis to cost \$12 and approximately 75mg of edible cannabis to cost \$15 (comparable across typical serving amount). However, this will depend in part on what cannabis type and how much cannabis each participant chooses to use. Study staff will not provide any directions regarding dosing and administration.

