an all THC, all CBD, and a combination of THC to CBD group [(+THC/-CBD, +THC/+CBD, and -THC/+CBD, ratios: 1:0, 1:1, and 0:1)].

[figure not shown]
[figure not shown]
To be conservative, we thus estimated an ICC of .50. Using a mixed model ANOVA design, with four groups, three assessment points, and an average ICC = .5 between assessment points, a total  $n=450$  (75 per flower group and the control, and 50 per edible group) will allow us to detect a groupXtime interaction effect as small as  $f=.09$ . In **Aim 2B**, the test of the effects of group on stress-reactivity will again involve four groups ( 3 cannabis and 1 control) but only one assessment point.. Note that our power analysis is conservative, as our actual analysis will involve more powerful tests (e.g., focused interaction contrasts as opposed to overall  $F$  tests). For **Aim 3**, the estimation of the mediational model via path analysis (Hypothesis 3; see Figures 3a and 3b below), Monte Carlo simulation strategies formed the basis of our power analysis. Given that the model in Figure 3b is the more complex of the two, we utilized the model structure with the three planned contrasts as exogenous variables in our simulations. The key test of Hypothesis 3 will involve the use of structural equation modeling techniques. Because we have almost no empirical data on which to base estimates of effect size, we conservatively utilized small to moderate effect sizes depending upon hypothesized relationships. For example, we expect small coefficients (.20) from each contrast to stress reactivity, whereas we expect a slightly larger path (.40) between the contrast comparing the -THC/+CBD strain to control and inflammation. Power analyses were conducted in Mplus and then in SAS following procedures for estimating the power of the likelihood ratio test of the significance of parameters in structural equation models. We utilized Monte Carlo simulation to generate a population covariance matrix based on the hypothesized parameters in the model. For the smallest path in the model (which requires the most power to test), assuming two-tailed alpha of .05, our estimates of power at various sample sizes appear in Table 3. To assure .80 power or better to detect small associations between all groups, we thus require data from 450 participants (75 in the control and each flower group as well as 50 in each edible group) for our mediational analyses.

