Daily Follow-Up Messages (Days 16-30)	Respond to brief questions (online) about cannabis use, sleep quality, and anxiety/stress management 1x/per day for 2 weeks after self-dosed cannabis use.	~2 mins/day x 15 days (~30 mins total)
4-Week Appointments (Mobile Lab)	Immediately before cannabis use (type and dose self-selected); Participant comes out to Mobile laboratory; Return completed microbiome kit, Physiological measures; Anxiety & Stress ratings; 3 rd Blood draw; Questionnaires; Cognitive & Motor Battery; Return home to self-administer edible.	60 mins
-Pre-administration Session 3		
-Post-administration Session 4	Immediately ( flower ) or 1-hour ( edible ) after self-dosing cannabis (time rage based on type of product chosen and similar drug onset time); Return to Mobile laboratory; Physiological measures; Anxiety & Stress ratings; 4 th Blood draw; Questionnaires; Cognitive & Motor Battery; Return wearable; Debriefing; Monetary Compensation; Return home.	60 mins
Monthly Follow-up Surveys (Months 2-6)	Respond to brief questions (online) about major behavioral changes (e.g., marijuana use, sleep quality, and anxiety/stress management) 1x/month for 5 months, Monetary compensation (each month).	~12 mins/month x 5 months (~60 mins total)

TOTAL TIME (6 months)	~8 hours
------------------------------	-----------------

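### Separate flower and edible cell sizes are stated, but the strain letter is balanced only on sex and no step records product form before the letter is issued

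*Combined protocol and SAP*

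**What the plan says.** **Cell sizes.** Section IV, Marijuana Administration at Home, gives "n=75/flower strain; n=50/edible strain". Power Analysis and Sample Size Requirements builds its total of 450 from "75 per flower group and the control, and 50 per edible group". The attrition paragraph inflates these to 86 per flower or control group and 58 per edible group.

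**Who decides form.** The design "allows participants to choose their type of administration". The Section IV overview places the ad libitum aspects outside the experimental element, "with regard to the dosing schedule and choice of product type (flower or edible").

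**How the letter is allocated.** The instruction to buy C, D or E is "randomized across participants such that equal numbers of male and female participants are included across the ratio conditions". No other balancing factor is named. The dispensary holds a flower lot and an edible lot of each strain. Of the card given to the participant, the text says: "The card will have instructions to purchase a particular strain of cannabis".

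**Order of events.** Section I and Section IV speak of flower users and edible users being assigned a ratio, and of people who opt for the edible group then being assigned an edible product. Table 1 lists strain assignment at Orientation, before the baseline measures. Marijuana Administration at Home puts the purchase instruction at the end of the baseline session, and Section XII puts assignment after the blood draw. The last table in Section XII describes Session 3 as "Immediately before cannabis use (type and dose self-selected").

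**The concern.** The plan commits to a size for each flower and edible cell but describes no mechanism that would produce those sizes. Balance on sex equalises sex across ratios. It does nothing for form, which a participant chooses and which is not said to be recorded before the letter is issued.

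Form matters because the products are not interchangeable. Section IV says that identical flower and edible potency groups cannot be assigned, and the post-use session is timed differently for the two forms. The Aim 1 model contains group, time and their interaction, with no term for form. A chance difference in form mix between strain arms would therefore be neither prevented by the allocation nor adjusted for. Any comparison within a form, or adjusted for form, would rest on cells of unplanned size. It would also rest on a classification with no stated time of measurement relative to assignment.

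**Working it through.** **1. The plan's own totals.**
- Analysed: 3×75 + 75 + 3×50 = 450, as stated. Users: 225 flower + 150 edible = 375, or 125 per ratio.
- Recruited: 4×86 + 3×58 = 518, against a stated figure of about 520. Users: 258 flower + 174 edible = 432, or 144 per ratio.
- The Section IV overview instead gives 450 users plus 75 controls. That is a separate discrepancy. The working below uses the sample-size section.

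**2. Form mix if letters ignore form: the case kindest to the plan.** Assume exactly 225 flower and 150 edible users, 125 per ratio, and form independent of ratio. The edible counts (a, b, c) in the three strains, with a + b + c = 150, then have probability

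C(125,a)·C(125,b)·C(125,c) / C(375,150).

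- SD of one cell: √[125 × 0.4 × 0.6 × (375−125)/(375−1)] = √20.05 = 4.48. The 95% range is 41 to 59 for an edible cell and 66 to 84 for a flower cell.
- A 10-point gap in edible share is 0.10 × 125 = 12.5, so a difference of 13 or more. P(largest minus smallest ≥ 13) = 0.24. For one given pair of strains, it is 0.11.
- P(smallest edible cell ≤ 44) = 0.32.
- P(all three edible cells exactly 50) = about 0.01.

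**3. The same events at the recruited numbers** (174 edible among 432, 144 per ratio).
- A 10-point gap is 14.4, so 15 or more: P = 0.19.
- 44 of 50 is 12% below target. 12% below 58 is 51.04, so 51 or fewer: P = 0.26.

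**4. If the form totals are also left to float.** The share choosing flower is not given; the cell sizes imply 60%. Treating it as an assumption, the detectable standardised difference between two edible cells (two-sided 0.05, 80% power) is d = (1.96 + 0.84) × √(2/n):

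| Assumed flower share | Expected flower / edible per ratio | Detectable d, two edible cells |
|---|---|---|
| 60% | 75 / 50 | 0.56 |
| 70% | 87.5 / 37.5 | 0.64 (38 v 38) |
| 80% | 100 / 25 | 0.79 |

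At a 50% share the expected cells are 62.5 / 62.5, so the flower cells fall short instead.

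**5. What is not affected.** The planned test has four groups, three assessments, an intraclass correlation of 0.5 and N = 450. With λ = f²·N·m/(1−ρ) = 0.0081 × 450 × 3 / 0.5 = 21.87 on 6 and 892 degrees of freedom, power at f = .09 is 0.96, and the f detectable at 80% power is 0.071. Form does not enter this calculation, and the pooled ratio arms stay at 125 whatever the form mix.

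**The case against.** The strongest reply is that the text already describes form first and ratio second. Sections I and IV refer to flower users and edible users being assigned, and recruitment is quoted separately by form. The randomisation sentence says what is balanced, not that nothing else is. This stands as evidence of intent. It does not supply a procedure: no step records the choice, no stratum uses it, and no recruitment rule holds the per-form totals.

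Second, every planned model pools the forms, so chance imbalance in form is not bias in the randomised ratio comparison, and the power statement survives. This stands in full and limits the weight of the point. The different post-use timing also falls outside the planned chronic-use analysis, which uses Sessions 1 to 3.

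Third, a reader might infer more than the documents support:
- **That participants choose form after reading the ratio on the label.** Section IV keeps participants and dispensary staff blind to ratio until purchase, so a first choice of form is not informed by ratio, even if made after the letter. A change at a later purchase could be, but nothing shows that it would be, and the daily reports ask for strain and method.
- **That the card names a letter and nothing else.** The card itself is not in the documents. The description gives a letter as an example.
- **That form is chosen afresh at week 4.** The Session 3 wording fits a form chosen at the outset equally well.

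**Conclusion.** The point holds as a gap in balance and procedure. The stated flower and edible cells are not secured by the allocation described. If letters ignore form, the chance of a 10-point or larger gap in edible share between two strains is about 24% at the analysed numbers and 19% at the recruited numbers. The chance of an edible cell at least 12% below target is about 32% and 26% respectively. These figures assume that the form totals land exactly on plan and that form is independent of ratio. Floating totals would move the cells further from their stated sizes.

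The exposure is confined to three things: chance imbalance in form between strain arms, the stated cell sizes, and any form-specific or form-adjusted comparison. The documents do not show that assigned ratio influences form, and the pooled four-group test is neither biased nor underpowered on this account. The change is worth making because it is cheap, not because the primary comparison is at risk.

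**What to change.** 1. At Baseline, record each user's intended form before the letter is issued.
2. Generate the C/D/E list in permuted blocks within form by sex (four strata).
3. Recruit to the stated per-form totals: 258 flower and 174 edible users, for 225 and 150 analysed.
4. In any analysis by form, keep each participant in the stratum of the declared form.
5. Do not make the declared form binding for the four weeks. Free choice of product type is a defended feature of the design, so capture later changes through the daily reports.
6. Reconcile Table 1 with Marijuana Administration at Home and Section XII on when assignment occurs. State whether type in the Session 3 row means the form declared at Baseline.

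With steps 1 to 3 the cells come out at 75 and 50, apart from incomplete blocks and uneven attrition. Total sample size and visits do not change. The cost is one extra Baseline field and a regenerated list, and recruitment may close for one form before the other.

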Marijuana-using subjects are prompted by email to report how much was used each day using an online reporting system (RedCap). We will also provide patients with safety information that will contain warnings regarding driving or operation of machinery, consistent with the warnings used with other over the counter and prescription drugs that may impact cognitive and motor functions (e.g., Benadryl, robitussin, benzodiazepines, narcotics, etc.). The important marijuana safety warnings will include: Do not drive, operate machinery, or perform other hazardous activities while using cannabis. It may cause dizziness, drowsiness, and impaired judgment. Do not drink alcohol while using cannabis. Alcohol will increase dizziness, drowsiness, and impaired judgment. Cannabis may increase the effects of other drugs that cause drowsiness, including antidepressants, alcohol, antihistamines, sedatives (used to treat insomnia), pain relievers, anxiety medicines, seizure medicines, and muscle relaxants. More information can be found on the National Institute of Health (NIH) DrugFacts page “What is marijuana?” (<https://www.drugabuse.gov/publications/drugfacts/marijuana>).

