Because the long-term goal of this work is to better understand the effect of different levels of cannabinoids in anxiety patients, as they are used real world, we decided that it was critically important to emphasize external validity in both the flower and edible forms of cannabis use. The disadvantage of our design is that we have little control over how the participants use the marijuana or how much they use. To address this limitation, both in our pilot study and in this application, we rely on blood quantitation of cannabinoids (from both flower and edible users) to determine the level of THC and CBD in each subject. Thus, regardless of how the participant uses the marijuana, we have an objective measure of the dose received for both THC and CBD for each subject, which is the sine qua non of pharmacological research. This aspect is also critical for our analytic approach, which allows for the analysis of THC and CBD blood levels as continuous measures. In this way, we also capitalize on the greater variability in blood levels expected in the design by analyzing overall levels of CBD and THC as well as by strain, which by design (in flower and edible forms) will have different THC/CBD ratios. This further allows for a direct test of whether any differences in outcomes for participants randomly assigned to the -THC/+CBD strain are due to an increase in CBD or a decrease in THC as compared to their Baseline. This strain is a critical comparison as there are data to suggest that the effects of THC differ when CBD is also in the blood.

**Power Analysis and Sample Size Requirements.** Sample size was selected to permit analysis of the primary research questions at two-tailed alpha of .05 and power level of .80. Estimates of effect size follow Cohen and were conducted in G\*Power 3. The primary analyses in **Aims 1-3** broadly is the test of the group X time interaction effects across repeated assessments of THC/CBD and anxiety, inflammatory markers, and stress reactivity. For the current data analysis plan, we will only focus on the ratios and time points that we currently have supporting preliminary data for and hypothesize to have the greatest impact on anxiety. Hence, in this data analysis plan we will focus on the 3 main time points (out of 4) for a chronic use endpoint [Baseline, 2 Week, and 4-Week Pre-administration (Sessions 1-3)] and the 3 main cannabis product so that there will be

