**COVID-19:** Before interacting with research assistants, eligible participants will be asked additional questions related to COVID-19. These questions will be administered prior to any in-person appointment and by a research assistant over the phone (or at a distance of at least 6-feet if the participant is unable to complete the questions over the phone). These questions will be administered to protect staff and participants from the spread of COVID-19. The questions are a precaution based on current university and Centers for Disease Control and Prevention guidelines and may need to be updated as the understanding of COVID-19 evolves. These procedural questions are temporary in nature and will be lifted once university guidelines deem it unnecessary.

**Baseline Appointment (Session 1) Procedures.** Subjects who meet inclusion criteria will be scheduled for a Baseline Appointment and given instructions for the assessments, including not consuming alcohol or marijuana for 24 hours, or caffeine for 4 hours prior to coming into the lab for their sessions. After arriving at the CUChange Lab, each subject will go through the consent process and be breathalyzed to ensure a breath alcohol concentration of zero. A urine toxicology screen (and a pregnancy test for females) will also be administered to insure that subjects have not recently taken illicit drugs (and are not pregnant). Menstrual cycles and birth control use will be reported. A baseline blood draw (see details below) will be taken to quantify inflammatory biomarkers and cannabinoids. A member of our research team who has completed a certified training in phlebotomy will collect a blood sample. All blood draw procedures performed during this study will involve collecting venous blood (40 ml total/session) venipuncture of a peripheral arm vein using standard, sterile phlebotomy techniques. Subjects will then be administered the Beck Anxiety Inventory (BAI), the State Trait Anxiety Inventory (STAI), the Depression, Anxiety, and Stress Scale (DASS), and complete measures related to alcohol/drug use history, mood, stress, and quality of life and will complete cognitive testing (see Table 2 below for measures to be completed).

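### Cannabinoid blood level at the analysed visits is an unvalidated proxy for four-week dose, and the blood-level models omit amount used, product form and recency

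*Combined protocol and SAP*

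**What the plan says.** All references are to the combined protocol and SAP.

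- **Section IV, Rationale for Marijuana Administration Procedure.** The plan names weak control over use as the design's disadvantage. Its remedy is blood quantitation: however the product is used, "we have an objective measure of the dose received for both THC and CBD for each subject". It then relies on blood levels to separate an increase in CBD from a decrease in THC relative to Baseline.
- **Section IV, Power Analysis and Sample Size Requirements.** The analysis plan is limited to a chronic-use endpoint at "Baseline, 2 Week, and 4-Week Pre-administration (Sessions 1-3"). The post-use Session 4 is left out.
- **Section XII, Baseline Appointment (Session 1) Procedures.** Participants receive instructions "including not consuming alcohol or marijuana for 24 hours, or caffeine for 4 hours prior to coming into the lab". The sentence goes on to refer to their sessions, in the plural.
- **Section XII, 2-Week and 4-Week Appointments, and the timetable closing Table 2.** Session 2 is in the same lab. Session 3 is in the mobile lab at the participant's home, immediately before use. The abstention instruction is not repeated for either.
- **Section XII, Blood Levels of Inflammation.** The post-use draw is timed by product form, at about 15 minutes for flower and one hour for edible, to allow for absorption.
- **Section IV, Specific Aims 1 and 2.** For Hypotheses 1 and 2A the exposure model has CBD in blood, time and their interaction. For Hypothesis 2B it has CBD in blood.
- **Use data.** "Marijuana-using subjects are prompted by email to report how much was used each day using an online reporting system". Table 1 lists amount, strain and method in the daily message. The Timeline Follow-Back (TLFB) in Table 2 records amount per day and method. Product potency is lab-tested and printed on the label.

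**The concern.** Each of Hypotheses 1, 2A and 2B has a second part that relates CBD and THC blood levels to the outcome, and the plan leans on that part to make up for ad libitum dosing. If the level follows four-week dose only loosely, the CBD slope is diluted. A null result would then have two explanations that the planned models cannot separate: CBD exposure has no association with the outcome, or the exposure was poorly measured. A positive slope would be open to question too, because it might reflect who used most recently, or who chose flower over edible, and not who used most.

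**Working it through.** **1. The plan's own figure.** No power figure is given for the blood-level tests. The only one for Aims 1 and 2 concerns group x time. The plan states: "Sample size was selected to permit analysis of the primary research questions at two-tailed alpha of .05 and power level of .80"; "with four groups, three assessment points, and an average ICC = .5 between assessment points"; N = 450 ("75 per flower group and the control, and 50 per edible group"); and that this "will allow us to detect a groupXtime interaction effect as small as" f = .09. With the usual repeated-measures formula:

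- λ = f²·N·m/(1−ρ) = .0081 × 450 × 3/.5 = 21.87
- df = (4−1)(3−1) = 6 and (450−4)(3−1) = 892
- power at f = .09 is .958, and the effect detectable at .80 is f = .071

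The stated .09 is not reproduced from these inputs, but it errs on the safe side and has no bearing on this point.

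**2. What each blood draw can reflect.**

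| Session | Blood timing in the documents | Consequence |
|---|---|---|
| 1 | Before strain assignment | A reference value; cannot reflect the assigned product |
| 2 | Two weeks in, same lab; abstention covered if the plural is read literally | Residual level |
| 3 | Mobile lab, immediately before use; abstention not stated | Residual level, time since last use unknown |
| 4 | After use, timed by product form | Acute level; outside the analysis plan |

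**3. How well a pre-use level could track dose.** The documents give no half-life, so I assumed a range and simulated 28 days of ad libitum use in 4,000 people per setting. Daily use probability was Beta(1.5, 1.5). Amounts were lognormal, with SD .7 between people and .5 between days. Elimination was first-order: level = Σ amount × 0.5^(hours since use/h). In the gap runs every use was moved back 24 hours.

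| Half-life h (hours) | 2 | 6 | 12 | 24 | 72 | 168 |
|---|---|---|---|---|---|---|
| Correlation with four-week dose, 24 h gap | .34 | .57 | .65 | .81 | .93 | .98 |
| Without the gap | .38 | .54 | .67 | .77 | .93 | .98 |

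A gap common to everyone multiplies every level by 0.5^(24/h) and cannot change a correlation, so the differences between the two rows are simulation noise. What drives the result is how fast the level falls after use. Everyone was given the same kinetics whatever the person or product form, so these figures are optimistic.

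**4. What that does to a test.** There are 3 × 75 + 3 × 50 = 375 users. For one two-sided correlation test at .05:

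- detectable r at .80 power = tanh((1.960 + .842)/√372) = .144 with perfect measurement
- if the level correlates q with true dose, the observed r is q × .144
- power = Φ(atanh(q × .144) × √372 − 1.960)
- N for .80 = (2.802/atanh(q × .144))² + 3

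| q (assumed) | Observed r | Power, n = 375 | N for .80 |
|---|---|---|---|
| 1 | .144 | .80 | 375 |
| .9 | .130 | .71 | 464 |
| .7 | .101 | .50 | 768 |
| .5 | .072 | .29 | 1,507 |
| .3 | .043 | .13 | 4,190 |

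This assumes that the measurement error is unrelated to the outcome. It also ignores the repeated assessments in the planned random coefficient models, so it shows sensitivity and is not the trial's power.

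**The case against.** The strongest reply is that the hypotheses are worded in terms of blood levels and the models test exactly that. Concentration set beside inflammatory markers from the same draw is a coherent exposure, and no hypothesis names cumulative dose. This stands, and it is why the blood-level models should be kept. It does not rescue the Rationale, which presents the level as the dose in order to answer uncontrolled use.

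Three further replies also stand. Session 1 blood is a legitimate baseline reference, and its timing is not a flaw. The limit to Sessions 1-3 comes from the power section, and applying it to the blood-level models is an inference, because the aims name no session. The half-lives are assumed, and at the long end (72 to 168 hours) the level would be a good marker.

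A reader might infer that the 24-hour abstention is what spoils the measure. The documents do not support that. The instruction sits under the Baseline procedures; its plural reasonably reaches Session 2, but for Session 3 it is only a guess. A uniform gap rescales levels without weakening their relation to dose, provided they stay measurable (no assay limit is given). If no abstention applies at Session 3, time since last use is uncontrolled and the problem remains.

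**Conclusion.** The point holds in a limited form. The plan equates blood level with dose received, but nothing in the design validates that for levels taken at Sessions 1-3, and the models have no term for amount, product form or recency. The possible loss runs from trivial to severe: a correlation with four-week dose of about .34 to .98 under half-lives of 2 to 168 hours and the use pattern assumed above. The documents do not allow a narrower range.

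Two stronger readings should be resisted. One is that blood level does not measure four-week dose at all; the upper end of the range contradicts that, and the right description is an unvalidated proxy. The other is that the trial's main comparison is compromised. The group x time tests across strains do not use blood level and are unaffected. The change is worth making because it is cheap and decides what a null or positive CBD slope can mean.

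**What to change.** 1. In the Rationale, describe the blood value as concentration at the visit, a marker of recent exposure, in place of dose received.
2. In Specific Aims 1 and 2, name the session or sessions supplying the blood level in each model. Reconcile the Baseline procedures with the 2-Week and 4-Week sections and the Table 2 timetable on which sessions the abstention instruction covers.
3. Add product form (flower or edible) to every blood-level model. Add recency at the resolution that the daily message and TLFB allow, namely days since last use.
4. Beside each blood-level model, run a sensitivity model on cumulative THC and CBD in mg, to Session 2 and to Session 3, from reported daily amount times labelled potency. Include product form as a covariate, or analyse the two forms separately.

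The cost is SAP wording and a derived variable from data already collected. Reported amounts carry recall error. Smoked and eaten milligrams are not interchangeable. Products used outside the assignment may lack a known potency. Clock time of last use is not described as collected, so recency will be coarse if levels fall quickly. Labelled potency also reveals the strain, and research staff are to stay blind until after data analysis. The variable should therefore be built by whoever holds the blind, or after the strain comparisons are complete.
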